7.8 Concomitant Medications and Other Therapy

For diabetic subjects, use of any diabetic medication other than metformin (generic or Glucophage®), GLP-1 agonists, SGLT2 inhibitors, sulfonylureas or DPP4 inhibitors 3 months prior to the diagnostic liver biopsy or during the study is prohibited. Subjects on metformin, GLP1 agonists, SGLT2 inhibitors, sulfonylureas or DPP4 inhibitors must have been stabilized on their current dose for a period of 3 months prior to diagnostic liver biopsy and the doses should not be altered during the study except as provided in the rescue medication instructions ([Section 6.4](#)).

Use of other prescription or over-the-counter (OTC) medications or herbal remedies is allowed during the study, as long as the subject has been stabilized on a dose for 6 weeks prior to study entry. Antiaggregants are allowed but should be discontinued for at least 5 days prior to the liver biopsy. Any concomitant medication taken during the study must be recorded in the eCRF.

Use of ursodeoxycholic acid is prohibited as there is insufficient knowledge of its effects in this subject population.

MSDC-0602K is metabolized to its hydroxymetabolite by a carbonyl reductase. This is a ubiquitous enzyme and there is no prior evidence to indicate that any concomitant medications would interfere with this metabolism. There is minimal interaction of MSDC-0602K or its metabolite with CYP P450 systems, either by direct inhibition or induction. However, there is a potential for inhibition of CYP2C8 and CYP2C9 particularly with the active metabolite, which is the predominant moiety in circulation. For these reasons, the following medications are also prohibited in this trial: paclitaxel, phenytoin, warfarin, celecoxib, tolbutamide and repaglinide.

7.9 Alcohol, Caffeine and Tobacco

Use of alcohol should be consistent with Exclusion Criterion 5 (no substance abuse within the past 6 months). If change in use of alcohol, caffeinated products or tobacco, as reported by the subject (not solicited by site at each visit), results in an adverse event, note this change in event term (e.g., headache from caffeine reduction, jittery from quitting or reducing tobacco use).

7.10 Physical Activity

Subjects will abstain from strenuous exercise other than normal activity (e.g., heavy lifting, weight training, calisthenics, or aerobics) for 48 hours prior to each blood collection for clinical laboratory tests. Walking at a normal pace will be permitted.

7.11 Dietary Guidance

Beginning at Visit 1, subjects who are not diabetics will be counseled to follow the NCEP Step 1 diet ([Appendix 2](#)). Subjects who are diabetic who have been following a diet consistent with ADA recommendations for type 2 diabetics ([Appendix 1](#)) should be counseled to continue that diet.

7.12 Meals and Fluid Intake

Subjects must abstain from all food and drink (except water) at least 10 hours prior to any safety laboratory evaluations and 10 hours prior to the start of PK sample collections.

7.13 Contraception

Only females who are postmenopausal (verified by FSH) or are surgically sterilized (bilateral tubal ligation, bilateral oophorectomy and/or hysterectomy) will be included in the study population; those with bilateral tubal ligation must use a barrier method of birth control during the study. Male subjects must use a condom, plus another form of contraception (e.g., spermicide, intrauterine device, birth control pills taken by female partner, diaphragm with spermicide) if engaging in sexual intercourse with a woman who could become pregnant. Male subjects must also be willing to abstain from sexual intercourse or use a condom during sexual intercourse with pregnant or lactating females. Male subjects must adhere to these contraceptive criteria from administration of study drug through the follow up visit on Day 374.

7.14 Premature Termination of Study/Closure of Site

The study may be terminated prematurely if new toxicological findings, or results affecting the safety of the subjects, become available. The sponsor reserves the right to terminate the study at any time for any reason.

A site may be closed based on issues identified with subject recruitment, GCP compliance, poor quality data, evidence of attempted or proven fraud, or for any reason at the sponsor's discretion.

In the event the sponsor prematurely terminates a particular study site, the site staff will promptly notify the Institutional Review Board (IRB).

8 STUDY DRUG

8.1 Investigational and Control Drugs

The sponsor will provide the following double blind study drugs:

- MSDC-0602K 62.5 mg capsules
- MSDC-0602K 125 mg capsules
- MSDC-0602K 250 mg capsules
- Matching Placebo #00 capsules

MSDC-0602K Tablets were manufactured by USV Limited, Daman, India. MSDC-0602K Capsules and Placebo Capsules were prepared, packaged and labeled by TEAM Pharmaceuticals, Kalamazoo, Michigan. All medication will be over-encapsulated in matching opaque capsules

and supplied to the Investigator as double-blind study drug in high-density polyethylene bottles (HDPE) with child resistant caps. Each bottle will contain medication for 31 days + 2 additional days of treatment. Three bottles/kit will be assigned and dispensed to each subject at each of Visits 1, 4, 5 and 6. Medication labels will include storage conditions for the drug and the subject's initials.

8.2 Treatments

At Visit 1 (Day 1), all eligible subjects will be equally randomized to one of the 4 treatment arms listed below:

- MSDC-0602K 62.5 mg capsules
- MSDC-0602K 125 mg capsules
- MSDC-0602K 250 mg capsules
- Matching Placebo #00 capsules

8.3 Randomization Code Creation and Storage

Randomization personnel of the sponsor or designee will generate the randomization schedule. All randomization information will be stored in a secured area, accessible only by authorized personnel.

8.4 Study Drug Blinding

The study is double-blind in that neither the subjects nor the Investigator will be aware of the treatment or dose administered. Blinding will be maintained throughout the study by use of active and placebo capsules of similar appearance. The series of random numbers from which the randomization algorithm operates will be created by personnel who will have no other involvement with analysis or statistical decision making for the study. The random number series will be sequestered from all blinded study personnel, assuring there will be no unblinding information available to them until the study completes.

8.5 Study Drug Assignment and Dispensing Procedures

At Visit 1 (Day 1), subjects who fulfill all the inclusion/exclusion criteria will be randomized to one of the 4 treatment arms using a stratification criterion based on presence of T2DM (Yes/No), use of Vitamin E \geq 400 IU (Yes/No) and fibrosis score (F1 or F \geq 2). The Investigator or his/her delegate will confirm that the subject fulfills all the inclusion/exclusion criteria prior to randomization. Treatment will be comprised of a 360-day double-blind period, followed by a 14-day safety follow-up period. Each subject is uniquely identified in the study by a combination of his/her center number and subject number. Only the assigned subject number should be entered in the field labeled "subject ID" on the electronic data capture (EDC) form. Once assigned to a subject, the subject number will not be reused.

Subjects, Investigator staff, and persons performing the assessments will remain blinded to the identity of the treatment from the time of randomization until database lock, using the following methods:

1. Randomization data are kept strictly confidential until the time of unblinding, and will not be accessible by anyone else involved in the conduct of the study (except for emergency unblinding as noted in [Section 8.9](#)).
2. The identity of the treatments will be concealed by the use of study drugs that are identical in packaging, labeling, and schedule of administration, appearance, taste and odor.

Data analysts, who are not directly involved with data management and monitoring of the trial, will remain blinded to individual treatment assignments until the interim analysis (see [Section 11.3.4](#)); an unblinded statistician may monitor the randomization process during the trial. The Interactive Response System (IXRS) will maintain a record that identifies each subject and the treatment/study drug of an individual subject's treatment assignment. Unblinding of all subjects' treatment assignments will occur at the conclusion of the trial following final database lock.

8.5.1 **Dispensing the Study Drug**

Each study site will be supplied by Sponsor or Designee with study drug in identically appearing packaging. The clinical supplies will be packaged and labeled in a double blind fashion. Medication will be supplied to the site in kits (containing 3 bottles per kit) for each subject. Each bottle will contain medication for 31 days + 2 additional days of treatment, and will have a total of 33 capsules per bottle. Three bottles will be packaged in a kit. A three bottle kit will be dispensed to subjects at Visits 1, 4, 5, and 6. Instructions will be provided in order to advise the site on the proper method of randomizing the subject and selecting the correct medication ID numbered kit/bottles for dispensing to a given subject at a specific visit. Sites will be resupplied additional kits as supplies diminish.

On Day 1, site personnel will administer the first dose of drug with approximately 240 mL of water following a minimum 10-hour overnight fast. The study drug kit will then be dispensed to the subject (1 kit containing 3 bottles each that will be dispensed at Visits 1, 4, 5 and 6). Subjects will be instructed to self-administer study drug once daily in the morning at least 30 minutes before the morning meal. They will be instructed to swallow the drug whole and not to chew or open the contents of the capsule.

One component of the packaging (kit) has a 2-part label. Each part of this label contains a medication ID number that will correspond to one of the treatment arms. Investigator staff will be informed which study drug package to dispense to the subject by contacting and obtaining the medication number via IXRS. Immediately before dispensing study drug to the subject, Investigator staff will detach the outer part of the label from the kits and affix them to the source document (Drug Label Form).

8.6 **Study Drug Interruptions**

Treatment interruptions should be avoided. A drug interruption occurring at any time during any period will be considered a protocol deviation. An occasional missed tablet is not considered treatment interruption. All changes will be recorded in the study records.

8.7 Compliance

Treatment compliance will be assessed using capsule counts conducted at Visits 4, 5, 6, and 7.

8.8 Study Drug Supply, Storage and Tracking

Study drugs must be received by a designated person at the study site, handled and stored safely and properly, and kept in a secured location to which only the Investigator and designated site staff have access. Upon receipt, all study drugs should be stored according to the instructions specified on the drug labels. Study drug must be kept in a secure cabinet or room with access restricted to only necessary study site personnel until it is used. Unused medication may be destroyed onsite with sponsor's approval or returned to the sponsor or designee for destruction. Clinical supplies are to be dispensed only in accordance with the protocol.

Medication labels will comply with the legal requirements of the U.S. They will include storage conditions for the drug, but no information about the subject. The Investigator must maintain an accurate record of the receipt of shipments and dispensing of study drug in a drug accountability ledger. Monitoring of drug accountability will be performed by the monitor during site visits and at the completion of the trial.

At the conclusion of the study, and as appropriate during the course of the study, the Investigator will return all used and unused study drug to the Sponsor or designee.

8.9 Emergency Unblinding

Unblinding is restricted to emergency situations and should be used only under circumstances where knowledge of the treatment is necessary for the proper management of the subject. When possible, the investigator should attempt to contact the medical monitor at Sponsor or designee before unblinding a subject's treatment assignment. The randomization code can only be broken if an emergency situation arises that, in the Investigator's opinion, requires knowledge of the drug product dosed for management of the emergency medical condition. To unblind a subject's treatment assignment, the investigator will access the unblinding module within the interactive response system. Instructions for breaking the blind will be provided to the site. Unless discontinued for a safety reason, study drug may be continued following unblinding of the subject's treatment assignment.

Copies of the randomization code will be made available to the analytical laboratory performing the PK analysis of plasma samples at the end of the study.

9 ADVERSE EVENTS

9.1 Adverse Events

The Investigator is to report all directly observed AEs and all AEs spontaneously reported by the subject using concise medical terminology. In addition, each subject will be questioned, in a non-directed manner about AEs at times specified in Table 1.

The AE reporting period for this trial begins upon signing of the informed consent form and ends at the final study visit (Visit 8).

All AEs that occur in subjects during the AE reporting period specified in the protocol, whether reported in response to a query, observed by site personnel, or reported spontaneously by the subject, must be recorded on the eCRF in the EDC system regardless of whether or not the event is considered medication related. Information to be collected and reported includes severity of the AE, relationship to study drug, duration of the AE, the treatment the subject is receiving at the time of the AE, and the outcome of the AE. The Investigator should attempt, if possible, to establish a diagnosis. For any AE which remains unresolved after completion of the study, the Investigator is responsible for following the AE to resolution or until a reasonable explanation for its persistence is found. In addition, any known untoward event that occurs subsequent to the adverse event reporting period that the Investigator assesses as possibly related to the investigational medication/product should also be reported as an adverse event.

9.1.1 Adverse Event Definitions

An AE is any untoward medical occurrence in a subject or trial subject that is administered a drug or biologic (medicinal product) or that is using a medical device; the event does not necessarily have a causal relationship with that treatment or usage. Adverse events include the following:

- All suspected adverse reactions
- All reactions from overdose, abuse, withdrawal, sensitivity, or toxicity.
- Apparently unrelated illnesses, including the worsening of a preexisting illness
- Injury or accidents. Note that if a medical condition is known to have caused the injury or accident (e.g., a fall secondary to dizziness or orthostasis), the medical condition (dizziness) and the accident (fall) should be reported as 2 separate adverse events. The outcome of the accident (e.g., hip fracture secondary to the fall) should be recorded in source documents.
- Abnormalities in physiological testing or physical examination findings that require clinical intervention or further investigation (beyond ordering a repeat test).
- Laboratory abnormalities that require clinical intervention or further investigation (beyond ordering a repeat test) unless they are associated with an already reported clinical event. Laboratory abnormalities associated with a clinical event (e.g., elevated liver enzymes in a subject with jaundice) should be captured in the source documents.

Each adverse event is to be classified by the Investigator as serious or non-serious. This classification of the gravity of the event determines the reporting procedures to be followed.

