2.2.2 Toxicology

The nonclinical safety profile of non-micronized MSDC-0602 was evaluated in rats and monkeys given once daily oral doses for up to 28 days (10,11). Pharmacokinetic studies of the micronized MSDC-0602 in the vehicle used in toxicology studies indicated that systemic exposures to both MSDC-0602 and MSDC-0597 were approximately 2.5-fold higher in rats and approximately 6-fold higher in monkeys than after administration of non-micronized compound. Consequently, the nonclinical safety profile of micronized MSDC-0602 was also evaluated in mice, rats and monkeys given once daily oral doses for up to 15 days. Subsequent pharmacokinetics studies demonstrated that even higher systemic exposure to both MSDC-0602 and MSDC-0597 was achieved following administration of MSDC-0602K (12,13). Since MSDC-0602K was selected for continued development, the nonclinical safety profile of MSDC-0602K was also evaluated in mice, rats and monkeys in repeated dose studies up to 52 weeks.

In 13-week studies, there were no MSDC-0602K-related deaths in mice given up to 2000 mg/kg/day (14) or in monkeys given up to 1000 mg/kg/day for 13 weeks (15). In the 13-week study in rats, 2 females given 2000 mg/kg/day had drug-related deaths; the highest nonlethal dose was 300 mg/kg/day (16). Decreases in red cell mass, and increases in liver and heart weight were observed in all 3 species; these effects were reversible. In rodents, the organ weight increases were accompanied by hepatocellular and cardiac myofiber hypertrophy. Increased adipocytes were seen in bone marrow in all 3 species, but hematopoietic cells were unaffected. Macrovesiculation of brown adipose tissue was noted in monkeys. There was biochemical and ultrastructural evidence of peroxisome proliferation in rats but not in monkeys. The NOAEL in the primary toxicology species, rats and monkeys, were 30 and 100 mg/kg/day, respectively. The mean combined-sex steady-state AUC₀₋₂₄ of pharmacologically active species (MSDC-0602 + MSDC-0597) at the NOAEL was 1,040,000 ng·hr/mL in rats and 549,000 ng·hr/mL in monkeys.

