9.1.4 Procedures

Diagnostic and therapeutic noninvasive and invasive procedures, such as surgery, should not be reported as AEs. However, the medical condition for which the procedure was performed should be reported if it meets the definition of an AE. For example, an acute appendicitis that begins during the adverse event reporting period should be reported as the AE and the resulting appendectomy should be recorded in the source documents. If a subject undergoes a surgical procedure that was planned prior to entry into the trial, and the surgery is not performed due to a worsening of a baseline (at the time of informed consent) condition, this should not be reported as an AE.

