7.9.8 Bone Fractures Requiring Surgery or Hospitalization

The number of fractures requiring surgery or hospitalization as well as the number and percentage of subjects with any fracture requiring surgery or hospitalization, as reported by the investigator, through 14 days after last dose of study treatment will be presented by treatment group.

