According to the protocol, sensitivity analyses had been planned for the primary and secondary dichotomous efficacy endpoints examining the addition of sex to the primary logistic regression

models. The sensitivity analyses have been updated to include age at baseline as well because age is expected to be associated with response, and to exclude use of Vitamin E ≥ 400 IU similar to the primary analysis. Further sensitivity analyses have been added to examine different time restrictions for the biopsies taken at 12 months.

Adjudication of Major Adverse Cardiovascular Events, liver events, and severe hypoglycemic events by a Clinical Events Committee, and collection of information regarding fractures were introduced after finalization of the protocol. Corresponding analyses have been added to the SAP.

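### Protocol 9.1.1 can lead sites to leave a fracture from a medically caused fall off the AE form, and the SAP fracture table does not pick it up unless it needed surgery or admission

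*Protocol*

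**What the plan says.** The relevant bullet of Protocol 9.1.1 opens by listing "Injury or accidents" among adverse events. It then deals with an accident known to have been caused by a medical condition. In its example, "the medical condition (dizziness) and the accident (fall) should be reported as 2 separate adverse events". The next sentence deals with the consequence: "The outcome of the accident (e.g., hip fracture secondary to the fall) should be recorded in source documents".

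Protocol 9.1 has a general rule that all AEs in the reporting period "must be recorded on the eCRF in the EDC system regardless of whether or not the event is considered medication related".

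SAP 7.9.1 builds its treatment-emergent tables, by system organ class and preferred term, from the AEs recorded on the eCRF. SAP 3.4 lists a fracture safety variable. SAP 7.9.8 tabulates it by arm, from investigator reports up to 14 days after the last dose, as "The number of fractures requiring surgery or hospitalization as well as the number and percentage of subjects with any fracture requiring surgery or hospitalization". No other fracture table is planned. SAP 8 explains that event adjudication and "collection of information regarding fractures were introduced after finalization of the protocol", without describing what that collection covers.

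**The concern.** The site rule and the two SAP outputs were written separately, and a fracture can fall between them. If the fracture is held only in source documents, it has no AE record to code. If it also needed neither surgery nor admission, it is outside the dedicated table.

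The sponsor has shown an interest in bone. Fracture is a named safety variable in SAP 3.4, and its collection was added after the protocol was final. Osteocalcin and CTX are exploratory endpoints (Protocol 4.2.3) and are part of the interim analysis (Protocol 11.3.4). In the 13-week animal studies, "Increased adipocytes were seen in bone marrow in all 3 species". Preliminary safety is part of the study objective. Few fractures can be expected in a 12-month trial of about 380 subjects, so a rule that loses some of them, or that sites apply unevenly, weakens any comparison between arms.

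**Working it through.** The documents contain no fracture rate and no figure to reproduce, so the check follows a fracture from the site to each output that could show it.

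**Step 1: what the recording rule means.** The 9.1.1 note gives each element of the event a place: the cause and the fall are AEs, and the outcome goes to source documents. The protocol does not say that the outcome goes only there. Its usage elsewhere points that way:

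- In 9.1.4 the appendicitis is the AE and "the resulting appendectomy should be recorded in the source documents".
- In 9.1.1 a laboratory abnormality belonging to a clinical event is also sent to source documents and is not a separate AE.

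In all three places the phrase marks something that is not entered as an AE in its own right. A site reading the protocol consistently would treat the fracture in the same way.

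**Step 2: trace to the outputs.**

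| Case | AE eCRF under 9.1.1 | AE tables (SAP 7.9.1) | Fracture table (SAP 7.9.8) |
|---|---|---|---|
| Medically caused fall; fracture without surgery or admission | Cause and fall | Cause and fall; no fracture | Not counted |
| Medically caused fall; fracture with surgery or admission | Cause and fall | Cause and fall; also a fall in the serious-event tables if classed as serious | Counted |
| Fracture from a simple trip, or without an accident | Not expressly covered by the note; the general rule applies | Fracture, if the site enters it | Counted only if surgery or admission |

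The first row is the gap: the fracture is tabulated nowhere as a fracture. In the second row the fracture is counted in 7.9.8, but the AE tables show a fall, so the two outputs would not agree. The third row depends on whether a site extends the note to all accidents. The sentence on outcomes refers simply to the accident, so sites could differ.

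**Step 3: whether the later collection closes the gap.** SAP 8 says that fracture information was added. The only analysis the SAP attaches to it is 7.9.8, with its restriction to surgery or admission. The eCRF is not among the documents, so it cannot be established whether other fractures are captured. If they are, the general listing rule in SAP 7.1 would put them in a subject listing by treatment group, but not in a table.

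**Step 4: size.** With 380 subjects in four equal arms there are 380 / 4 = 95 per arm. Purely as an assumption, with 1% to 3% of subjects having any fracture in the year, 95 x 0.01 = 0.95 to 95 x 0.03 = 2.85 fractures of all kinds would be expected per arm. The untabulated fractures are some unknown part of that number.

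**The case against.** The strongest reply is that the protocol never tells sites to keep the fracture off the eCRF. Injuries are listed as AEs, every AE must go on the eCRF, and any fracture entered there will appear in the AE tables. The note is also conditional on a medical condition having caused the accident, so many fractures lie outside it. All of this is correct. It limits the point to the note's own condition and makes the loss possible rather than certain. It does not remove the problem, because the fracture sentence sits inside the injury bullet as the more specific instruction. If sites resolve the two differently, the counts are still unreliable.

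A second reply is that limiting a supplementary table to fractures needing surgery or admission is a defensible choice and that the table is labelled as such. That also stands. The table does not claim to show all fractures, and the restriction would matter less if the AE tables reliably held the rest.

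A third reply is that the bone interest is modest. The turnover markers are exploratory efficacy endpoints, the animal findings in the chronic studies were not considered adverse, and the women enrolled include those with tubal ligation, which does not by itself indicate skeletal risk. This is fair, and it is why the case rests on the sponsor's own fracture variable and not on an asserted hazard.

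A reader might infer that all fall-related fractures treated as outpatients are missing from the safety outputs, or that a given share of fractures will be lost. The documents support neither. The word only is an inference, the scope is conditional, and no rate or share is given.

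**Conclusion.** The point holds as a gap in recording and tabulation. When a medical condition causes a fall, following 9.1.1 as written can leave the resulting fracture without an AE record. If it was managed without surgery or admission, no planned table shows it as a fracture. If it led to admission, the AE and serious-event tables may show only the fall. The fall itself is always reported.

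This rests on two readings: that the contrast with the two reported AEs steers sites away from entering the fracture, and that the later fracture collection has no wider scope than the SAP describes. The second cannot be verified without the eCRF.

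The size of the loss is unknown. A reader might infer that full capture would allow a conclusion of no fracture signal. It would not: under the assumed 1% to 3%, about one to three fractures per arm are too few for that. The gain is a count that is complete and recorded in the same way at every site. The change is worth making because it is cheap, not because the present plan invalidates the safety assessment.

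**What to change.** 1. Amend Protocol 9.1.1, or the eCRF completion guidelines, so that any fracture is entered as an AE on the eCRF in addition to the accident and its cause.
2. Query all sites once, blinded to treatment and before database lock, to enter fractures held in source documents. Retrieval after unblinding would be open to bias.
3. Add a row for all reported fractures to the SAP 7.9.8 table, with the matching variable in SAP 3.4. Keep the present row for fractures needing surgery or hospitalization.

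The cost is one sentence, one round of queries and one table row. The total will include minor fractures and so be less specific, but the existing row preserves the figure now planned.
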